6.6 TREATMENT CODE

This is an open-label study. The randomisation list will be generated as reported in [Section 6.5](#) and distributed to the contract research organisation (CRO) and the investigational site.

The randomisation list will be kept in the Trial Master File.

6.7 TREATMENT COMPLIANCE

Compliance to each treatment will be evaluated on the basis of the information reported by the Investigator (for the treatment administrations on the morning of Day 1 and the morning of Day 8 of each treatment period) and the subjects’ DRC (for the treatment administrations from the evening of Day 1 to the evening of Day 7, see [Section 7.2.7](#)).

The evaluation of compliance will be done using the following formula:

$$\frac{\text{TOTAL NUMBER OF ADMINISTERED INHALATIONS}}{\text{TOTAL NUMBER OF SCHEDULED INHALATIONS}} \times 100 = \% \text{ OF ADMINISTERED INHALATIONS}$$

The total number of scheduled inhalations will be calculated on the basis of the extent of exposure of each subject (8 days for each treatment period). A range of 80% will be taken into account for a satisfactory level of compliance.

6.8 DRUG STORAGE

The Pharmacist/Investigator will be responsible for the safe storage of all medications assigned to this study. Study medications are to be stored in a locked, secure storage facility with access limited to those individuals authorised to dispense them.

The following storage conditions must be respected:

- **Treatment kits** (placebo HFA-152a propellant pMDI and placebo HFA-134a propellant pMDI): the subject box must be stored in a refrigerator at a temperature between 2°C and 8°C. In the morning of Day 1 of TP1, only the period box must be removed from the refrigerator, while the subject box must be maintained in the refrigerator until Day 1 of TP2. At Day 1 of each treatment period, at discharge, the period box will be dispensed to the subjects. Subjects will be advised to keep the period box at ambient temperature: not above

Clinical Study Code No.: CLI-05993AB6-06

Version No.: 1.0

Date: 16 February 2023

EudraCT number: 2022-003247-97

25°C and not in the refrigerator. At ambient temperature, the residual shelf life of the pMDI kit is of 2 months (60 days). Therefore, once the kit is removed from the refrigerator and before dispensing it to the subject, the Pharmacist/Investigator must write the use-by date (i.e. dispensing date plus 2 months) on the kit labels. The use-by date must not exceed the total shelf life of the product.

- **Training kit** (placebo HFA-134a propellant pMDI): before being used, kits must be stored in a refrigerator, at a temperature between 2°C and 8°C.

At screening (V1), the training kit to be used must be removed from the refrigerator. At ambient temperature, the residual shelf life of this pMDI is of 3 months (90 days). Therefore, the Pharmacist/Investigator must write the use-by date (i.e. date of the screening visit [V1] plus 3 months) on the kit labels. The use-by date must not exceed the total shelf life of the product.

Once used, the training kits must be kept at the investigational site at ambient temperature (not above 25°C and not in the refrigerator) and should not be dispensed to the subjects.

In case of study medication exposed to temperatures outside the required temperature range, Chiesi or delegate shall issue the assessment of its usability which shall either release the quarantined study drug or declare its permanent non-usability.

6.9 TREATMENT ACCOUNTABILITY AT SITE

The Investigator or a designated/authorised representative is responsible for the management of all the study medications to be used for the study. Study medications should be stored in a locked, secure storage facility with access limited to those individuals authorised to dispense the study medications.

An inventory will be maintained by the Investigator or Pharmacist (or other designated individual), to include a signed account of all the study medications received, dispensed, and returned by each subject during the study.

At the conclusion or termination of the study, the Investigator or Pharmacist shall conduct and document a final inventory of the drug supply (used and unused). An explanation will be given for any discrepancies.

All the study medications, supplied, used or unused, will be destroyed by the Investigator, directly at the investigational site. In this case, a destruction certificate must be requested from the investigational site and must be filed, both at the investigational site and by the Sponsor. Destruction will not occur until authorised by Chiesi.

6.10 PROVISION OF ADDITIONAL CARE

Not applicable, the study will be conducted in healthy subjects.

6.11 HOME VISITS

Not applicable.

7. STUDY PLAN

7.1 STUDY SCHEDULE

The study will be conducted as described in [Section 3](#) and [Table 2](#).

Current UK national laws and site-specific recommendations for the prevention of the COVID 19 pandemic will be strictly adhered to. These include subjects' monitoring for COVID-19 symptoms

Clinical Study Code No.: CLI-05993AB6-06	Version No.: 1.0	Date: 16 February 2023
EudraCT number: 2022-003247-97		

and the adherence to the appropriate measures to control the transmission of the virus in the clinical setting [24].

The study plan and scheduled tests are summarised in [Table 2](#).

The execution order of the study treatment administration and of the cardiac (ECG and vital signs), pulmonary (lung function) and MCC assessments on Day 8 of each treatment period is further specified in [Table 3](#).

Clinical Study Code No.: CLI-05993AB6-06	Version No.: 1.0	Date: 16 February 2023
EudraCT number: 2022-003247-97		

Table 2. Schedule of assessments

	Screening visit (V1)	Investigational Phase (TP1 and TP2) ^[1]				Early termination visit	Follow-up call ^[2]
		V2/V5	V3/V6	V3 to V4 V6 to V7	V4/V7		
Date	2-21 days before V2	Day -1	Day 1 (morning)	Day 1 (evening) to Day 7 (evening)	Day 8 (morning)		7-10 days after last intake of study treatment
Informed consent	X						
Randomisation			X (TP1 only)				
Ambulatory visit	X	X	X		X	X	X ^[2]
Treatment intake							
Treatment administration ^[3]			X	X	X		
Training							
Placebo training	X						
Training with AIM TM	X						
Subject health evaluation							
Inclusion/Exclusion criteria	X	X (TP1 only)	X (TP1 only)				
Medical history and previous medications	X						
Demographic data	X						
Height and weight	X						
Body temperature	X	X	X		X	X	
Physical examination	X		X		X (TP2 only)	X	
Alcohol breath test	X	X			X	X	
Adverse events recording	X	X	X	X	X	X	X
Restrictions	X	X	X	X	X	X	
Concomitant medications	X	X	X	X	X	X	X

Clinical Study Code No.: CLI-05993AB6-06	Version No.: 1.0	Date: 16 February 2023
EudraCT number: 2022-003247-97		

	Screening visit (V1)	Investigational Phase (TP1 and TP2) ^[1]				Early termination visit	Follow-up call ^[2]
		V2/V5	V3/V6	V3 to V4 V6 to V7	V4/V7		
Date	2-21 days before V2	Day -1	Day 1 (morning)	Day 1 (evening) to Day 7 (evening)	Day 8 (morning)		7-10 days after last intake of study treatment
Safety assessments in blood							
Clinical chemistry	X				X (TP2 only)	X	
Serology	X						
Haematology	X				X (TP2 only)	X	
Fasting glucose	X				X (TP2 only)	X	
FSH or pregnancy test ^[4]	X						
Generic assessments in urine							
Urinalysis	X						
Cotinine test	X	X			X	X	
Drug panel test	X	X			X	X	
Pregnancy test ^[4]		X			X (TP2 only)	X	
Cardiac assessments ^[5]							
12-lead ECG	X		X		X	X	
Vital signs	X		X		X	X	
Pulmonary assessment							
Lung function ^[6]	X		X		X		
MCC assessment ^[7]							
Co-57 transmission scan and background scan		X (TP1 only)					
Administration of radiotracer and image acquisition		X			X		

Clinical Study Code No.: CLI-05993AB6-06	Version No.: 1.0	Date: 16 February 2023
EudraCT number: 2022-003247-97		

	Screening visit (V1)	Investigational Phase (TP1 and TP2) ^[1]				Early termination visit	Follow-up call ^[2]
		V2/V5	V3/V6	V3 to V4 V6 to V7	V4/V7		
Date	2-21 days before V2	Day -1	Day 1 (morning)	Day 1 (evening) to Day 7 (evening)	Day 8 (morning)		7-10 days after last intake of study treatment
Other assessments							
Daily record card ^[8]				X			

BID=Twice daily; Co-57=57-Cobalt; DBP=Diastolic blood pressure; ECG=Electrocardiogram; eCRF=Electronic case report form; FEV₁=Forced expiratory volume in 1 second; FSH=Follicle-stimulating hormone; FVC=Forced vital capacity; MCC=Mucociliary clearance; SBP=Systolic blood pressure; SpO₂=Oxygen saturation levels; TP=Treatment Period; V=Visit; WOCBP=Women of childbearing potential.
 
[1] TP1 and TP2 will be separated by a 7- to 14-day wash-out period.
 
[2] A follow-up visit (instead of a call) can be performed, if deemed necessary by the Investigator. A follow-up call (or visit) will be performed in case of early termination as well, if the early termination visit is performed less than 7 days after the intake of the last dose of the study treatment.
 
[3] A total of 5 inhalations BID for 8 consecutive days, starting from the morning of Day 1 until the morning of Day 8. The first and last dose of the study treatment will be administered at the investigational site.
 
[4] For logistical reasons, both the pregnancy test (in blood and urine) and FSH test will be performed for samples collected from all female subjects. However, only the relevant results will be recorded in the eCRF (i.e. pregnancy tests for WOCBP and FSH tests for post-menopausal women).
 
[5] Cardiac assessments will be performed before the lung function assessments and the blood tests, and as described below:
 
 • Vital signs: At screening, SBP and DBP (in duplicate, made within a 5-minute interval) will be evaluated after 5 minutes in supine position. On the morning of Day 1 and Day 8 of each treatment period, SBP, DBP (in duplicate) and SpO₂ (in single) will be evaluated at the following timepoints: 
 ○ Pre-dose: within 1 hour before the intake of the first inhalation of the propellant; ○ Post-dose: 5 minutes, 15 minutes, 1 hour 45 minutes after the intake of the last inhalation of the propellant. • Local 12-lead safety ECG: a triplicate ECG will be performed to assess eligibility at screening (V1) and a single ECG will be evaluated on the morning of Day 1 and Day 8 of each treatment period, at the same timepoints (before or after) as the vital signs. 
In case of early termination, SpO₂ (single), SBP and DBP (duplicate) will be assessed and a single local 12-lead ECG will be measured during the early termination visit.
							

Clinical Study Code No.: CLI-05993AB6-06	Version No.: 1.0	Date: 16 February 2023
EudraCT number: 2022-003247-97		

	Screening visit (V1)	Investigational Phase (TP1 and TP2) ^[1]				Early termination visit	Follow-up call ^[2]
		V2/V5	V3/V6	V3 to V4 V6 to V7	V4/V7		
Date	2-21 days before V2	Day -1	Day 1 (morning)	Day 1 (evening) to Day 7 (evening)	Day 8 (morning)		7-10 days after last intake of study treatment

[6] Lung function assessments (spirometry [FEV₁ and FVC]) will be performed as follow:

- Screening: single spirometry to assess the subject's eligibility;
- On the morning of Day 1 and Day 8 of each treatment period, spirometry assessments will be performed as follow:
 - Pre-dose: within 30 minutes before the intake of the first inhalation of the propellant;
 - Post-dose: 20 minutes after the intake of the last inhalation of the propellant.

[7] MCC assessments will be performed as follow:

- Co-57 transmission scan and background scan: Day -1 of TP 1 only, prior to the assessment of MCC;
- Administration of radiotracer and image acquisition: subjects will be administered a radiotracer and image acquisitions will be performed at 0 (immediately), 15 minutes, 30 minutes, 1 hour, 1 hour 30 minutes, 2 hours, 2 hours 30 minutes, 3 hours and 4 hours after the administration of the radiotracer. The analysis of these images will provide a measurement of MCC.
On Day 8 of each treatment period, the radiotracer will be administered approximately 2 hours after the administration of the last dose of the propellant.

[8] Subjects will use a daily record card (one for each treatment period) to record the intake of the study propellant, the occurrence of adverse events or the intake of concomitant medications. The daily record card will be given to the subjects on Day 1 of each treatment period and will be collected on Day 8 of each treatment period. In case of early discontinuation, if discontinuation occurs during a treatment period, the daily record card will be collected during the early termination visit.

Clinical Study Code No.: CLI-05993AB6-06

Version No.: 1.0

Date: 16 February 2023

EudraCT number: 2022-003247-97

Table 3. Assessment execution order on Day 8 of each treatment period

Execution order	Task	Timepoint (± acceptable time window)	Reference time
1	Pre-dose ECG and vital signs	Within 1 h	First inhalation of propellant
2	Pre-dose lung function	Within 30 min	
3	Inhalation of propellant	NA	
4	ECG and vital signs	5 min ± 5 min	Last inhalation of propellant
5	ECG and vital signs	15 min ± 5 min	
6	Lung function	20 min ± 5 min	
7	ECG and vital signs	1h 45 min ± 15 min	
8	Administration of radiotracer	Approximately 2 h	
9	Image acquisition	0 min ± 2 min	End of radiotracer inhalation
10	Image acquisition	15 min ± 5 min	
11	Image acquisition	30 min ± 5 min	
12	Image acquisition	1 h ± 5 min	
13	Image acquisition	1 h 30 min ± 5 min	
14	Image acquisition	2 h ± 5 min	
15	Image acquisition	2 h 30 min ± 5 min	
16	Image acquisition	3 h ± 5 min	
17	Image acquisition	4 h ± 5 min	

ECG=Electrocardiogram; h=hour; min=minute; NA=Not applicable.

Clinical Study Code No.: CLI-05993AB6-06

Version No.: 1.0

Date: 16 February 2023

EudraCT number: 2022-003247-97

7.1.1 SCREENING (V1)

A screening visit will be carried-out in order to identify eligible consenting subjects for the study.

The screening visit will take place 2 to 21 days before the start of the Investigational Phase (Day -1 of TP1).

The following procedures will take place at screening:

- Informed consent: a signed ICF will be obtained from potential eligible subjects, after a full and detailed description of the study by the Investigator. The Investigator or his/her designee should provide subjects with ample time and opportunity to inquire about details of the study and to decide whether or not to participate in the study. The ICF has to be signed before the start of any study-related procedures (see [Section 15](#));
- Demographic data collection: demographic data including age, gender and race will be recorded;
- Physical examination: a full physical examination will be performed;
- Medical/surgical history, concomitant diseases and previous medications: subjects' medical and surgical history, as well as concomitant diseases (i.e. diseases pre-existing at the time of the ICF signature) will be recorded. Any medications taken in the 3 months preceding the screening visit will be recorded;
- Study restrictions: study restriction criteria and adherence to the wash-out requirements applicable before the spirometry assessments and blood tests will be checked according to [Section 4.4](#);
- Concomitant medications: any medication taken regularly at the time of this visit will be recorded;
- AE recording: AEs that have occurred since the ICF signature will be recorded in the eCRF, along with the related concomitant medications.
In cases where clinically significant (CS) abnormalities are revealed during the physical examination or screening procedures, these will be recorded in the subject's eCRF as medical history, unless the start date/time is after the ICF signature date/time and it is not due to a pre-existing condition. In the latter case, it will be recorded in the eCRF as an AE;
- Local safety ECG: triplicate 12-lead ECG will be used to measure HR, QRS, PR and QTcF. The assessment will be performed according to [Section 7.2.4](#);
- Vital signs: SBP and DBP will be measured according to [Section 7.2.3](#);
- Body temperature: will be assessed according to [Section 7.2.3](#);
- Blood test: blood samples will be collected for safety evaluations (clinical chemistry, serology, haematology and fasting glucose), after the 12-lead ECG and vital signs assessments, according to [Section 7.2.5](#);
- FSH or pregnancy tests: blood samples will be collected from female subjects for FSH and serum pregnancy tests, according to [Section 7.2.5](#);
- Urine test: urine samples will be collected for urinalysis and for urine cotinine and drug panel test (according to [Section 7.2.6](#));
- Alcohol breath test: will be performed using a specific kit;
- Height and weight: will be recorded;
- Lung function: single spirometry will be performed (after the ECG records and the assessment of the vital signs), according to [Section 7.2.2](#);

Clinical Study Code No.: CLI-05993AB6-06

Version No.: 1.0

Date: 16 February 2023

EudraCT number: 2022-003247-97

- Training: subjects will receive training on the proper use of the inhaler with the AIM™ Vitalograph and a pMDI placebo, according to [Section 6.1.2.4.1](#) and [Section 6.1.2.4.2](#), respectively;
- Subject selection: inclusion/exclusion criteria will be checked (see [Section 4.2](#) and [Section 4.3](#), respectively).

Before discharge, subjects will be given the following instructions:

- To adhere to the study restrictions and to the pre-MCC wash-out requirements before coming to V2, according to [Section 4.4](#);
- To avoid taking any of the non-permitted concomitant medications, according to [Section 5.2](#).

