The selected treatment dose (i.e. 5 inhalations BID) corresponds to the maximum total daily dose of HFA-134a propellant allowed for administration with the Clenil pMDI device, according to the current summary of product characteristics (SmPC) (for Clenil 100 µg, the maximum allowed daily dose is 1000 µg, administered as 500 µg BID).

The effect on MCC of each propellant will be evaluated by the change, from baseline (before administration of each propellant) to the end of the 8-day treatment period, in the percent particle retention (PPR) evaluated at 0 (immediately), 2 and 4 hours after the administration of a radiotracer.

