6.1 TREATMENTS BEING INVESTIGATED

6.1.1 APPEARANCE AND CONTENT

Test treatment: placebo HFA-152a propellant pMDI, presented as:

- Active ingredients: none;
- Excipients: HFA-152a propellant, [REDACTED];
- Presentation: each canister contains 120 doses;
- Appearance: aluminium canister + grey actuator.

Reference treatment and training kit: placebo HFA-134a propellant pMDI*, presented as:

- Active ingredients: none;
- Excipients: HFA-134a propellant, [REDACTED];
- Presentation: each canister contains 120 doses;
- Appearance: aluminium canister + grey actuator.

*For this study, CHF 1535 placebo HFA-134a propellant pMDI will be used.

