6.1.2.4.2 Training with Pressurised Metered Dose Inhaler Placebo

At screening, the correct use of the pMDI device will be explained to the subjects according to the instructions for use (provided in a separate document).

Subjects will be trained by using a placebo HFA-134a inhaler, which is identical from a functional point of view to the device used for the administration of the study treatments (see [Section 6.3.2](#)). Therefore, the training will be done with the pMDI device, with the inhalation repeated five times or as many times as necessary until the subject is properly trained.

Clinical Study Code No.: CLI-05993AB6-06

Version No.: 1.0

Date: 16 February 2023

EudraCT number: 2022-003247-97

The training kits will be kept at the investigational centre by the Investigator and will not be dispensed to the subjects. The training kit will be assigned to the subject at screening.

The subject will not be included in the study if the training is not completed successfully. Training evidence will be recorded in the eCRF by the Investigator or designee.

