7.1.2 INVESTIGATIONAL PHASE

The Investigational Phase will comprise two 9-day treatment periods (TP1 and TP2), separated by 7 to 14 days of wash-out from the propellant. Each treatment period will consist of 3 ambulatory visits at the investigational site.

7.1.2.1 TREATMENT PERIOD 1

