7.1.2.2.1 DAY -1 OF TREATMENT PERIOD 2 (V5)

V5 is the first visit of TP2. It takes place after a 7- to 14-day wash-out period from the propellant administered during TP1.

The following procedures will take place at this ambulatory visit:

- **Study restrictions:** study restriction criteria and adherence to the wash-out requirements applicable before the MCC assessment will be checked, according to [Section 4.4](#);
- **Alcohol breath test:** will be performed using a specific kit;
- **Concomitant medications:** concomitant medications taken by the subject since the previous visit and during V5 will be checked and recorded;

Clinical Study Code No.: CLI-05993AB6-06

Version No.: 1.0

Date: 16 February 2023

EudraCT number: 2022-003247-97

- Urine test: urine samples will be collected for urine cotinine and drug panel test, according to [Section 7.2.6](#);
- Pregnancy test: urine samples will be collected from female subjects for pregnancy testing, according to [Section 7.2.6](#);
- Body temperature: will be assessed according to [Section 7.2.3](#);
- AE recording: the status of AEs ongoing at V4 will be checked and updated in the eCRF when applicable. Any new AE occurring since the previous visit will be checked and recorded in the eCRF, as well as the related concomitant medications. Any AE occurring during the study visit must also be monitored and recorded in the eCRF;
- MCC assessment: subjects will be administered a radiotracer. Image acquisitions for the assessment of MCC will be performed at 0 (immediately), 15 minutes, 30 minutes, 1 hour, 1 hour 30 minutes, 2 hours, 2 hours 30 minutes, 3 hours and 4 hours after the administration of a radiotracer, according to [Section 7.2.1](#).

Before discharge, subjects will be given the following instructions:

- To adhere to the study restrictions and to the pre-spirometry wash-out requirements before coming to V6, according to [Section 4.4](#);
- To avoid taking any of the non-permitted concomitant medications, according to [Section 5.2](#).

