## 5.2 PHASES, PERIODS AND TIME POINTS

### 5.2.1 *Phases and periods*

Adverse events, medications, and procedures will be allocated to phases and periods. All other analyses will not be allocated to phases and periods. Instead, the visit and time point labels indicated on the subject's electronic case report form (eCRF) will be used to allocate the assessments to the correct treatment. Early termination and follow-up visit assessment will be allocated to the last administered treatment.

Adverse events and medications:

Phase	Period	Start	End
Screening		Date of signing the informed consent form (ICF), with 00:00 added as time part	First administration date(time) in the first available period – 1 minute
Treatment	Period 1	First administration date(time) in period 1	First administration date(time) in the next available period – 1 minute
	Period 2	First administration date(time) in period 2	Date of last contact, with 23:59 added as time part

Per definition, and for each subject, the first phase starts on the date of the earliest available ICF signature, with 00:00 added as time part. The last available phase/period ends on the date of last contact, with 23:59 added as time part.

Procedures:

Phase	Period	Start	End
Screening		Date of signing the informed consent form (ICF)	First administration date in the first available period – 1 day
Treatment	Period 1	First administration date in period 1	First administration date in the next available period – 1 day
	Period 2	First administration date in period 2	Date of last contact

Per definition, and for each subject, the first phase starts on the date of the earliest available ICF signature. The last available phase/period ends on the date of last contact.

All tables and figures will present treatments rather than periods.

	Statistical Analysis Plan	
CLI-05993AB6-06	Final Analysis	Final 1.0 of 05OCT2023

AEs, medications and procedures will be allocated to phases and periods as described in sections 3.1.2 and 4.5.2 respectively.

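### The two Day -1 baseline scans have different minimum propellant-free intervals (2 days after HFA-134a training, 7 days after Period 1), and no planned table or figure compares them within subject

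*Protocol*

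**What the plan says.** **Training.** Protocol 6.1.1 describes one product for two uses: "Reference treatment and training kit: placebo HFA-134a propellant pMDI". Section 6.1.2.4.2 confirms that "Subjects will be trained by using a placebo HFA-134a inhaler" at screening, "with the inhalation repeated five times or as many times as necessary until the subject is properly trained". One study dose is five inhalations, so training is at least one dose and has no upper limit.

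**Interval to the first baseline.** Protocol 7.1.1: "The screening visit will take place 2 to 21 days before the start of the Investigational Phase (Day -1 of TP1").

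**Interval to the second baseline.** Protocol 7.1.2 has the periods "separated by 7 to 14 days of wash-out from the propellant". Section 7.1.2.2.1 says of V5: "It takes place after a 7- to 14-day wash-out period from the propellant administered during TP1".

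**Meaning of baseline.** Protocol 1.2 evaluates each propellant by the change "from baseline (before administration of each propellant) to the end of the 8-day treatment period". SAP 5.2.2 defines baseline relative to study treatment within each period, so training does not count. The restrictions before MCC visits (Protocol 4.4) concern nicotine, alcohol, caffeine, exertion and clothing, not training inhalations.

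**Analysis and display.** SAP 2.1.3 reports an adjusted mean change for each propellant, and their difference, with 95% CIs and p-values. The model has treatment, period, fixed subject and the period's own baseline. SAP 5.2.1: "All tables and figures will present treatments rather than periods". The MCC tables and figures in SAP 8.1 and 8.3 follow that rule. Both Day -1 scans of a subject appear together only in Listing 16.2.6.1.

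**The concern.** The primary objective asks for the effect of both propellants on clearance, so each propellant's own change is a primary result, not only the contrast. That change is interpretable only if Day -1 reflects undisturbed clearance. The plan allows propellant 2 days before one baseline and requires at least 7 days before the other, without giving a reason for the difference.

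If slowed clearance persisted to Day -1, baseline retention would be too high and the change to Day 8 too small, so the propellant would look more benign than it is. The study collects the data that bear on this, Day -1 retention in both periods, but plans no within-subject comparison of them. Fixed subject effects absorb sequence, so the model has no term that would isolate carry-over.

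**Working it through.** **Exposures.** SAP 4.6.2 schedules 5 × (2 × 8 − 1) = 75 inhalations in a completed period. Training is 5 or more.

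**Kinetics.** Protocol 1.1 gives a mean residence time of about 9 minutes for HFA-152a. Two days is 2 × 1440 / 9 = 320 residence times; seven days is 7 × 1440 / 9 = 1120. This concerns the gas, not recovery of mucociliary function, and no such figure is given for HFA-134a.

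**Bias.** Assume residues that raise retention at Day -1 and are gone by Day 8:
- e: training residue in the Period 1 baseline, all subjects;
- lT, lR: residues of HFA-152a and HFA-134a in the Period 2 baseline of subjects who received them first.

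Half the subjects receive each propellant in each period, so the raw mean changes shift by:
- HFA-152a: −(e + lR)/2
- HFA-134a: −(e + lT)/2

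The average of the two adjusted changes shifts by −[e + (lT + lR)/2]/2. Let ρ be the within-period correlation of Day -1 and Day 8 beyond the subject effect. The model's slope of change on baseline is then ρ − 1. The raw contrast shifts by (lT − lR)/2 and the Day -1 means differ by (lR − lT)/2, so the adjusted contrast shifts by (lT − lR)/2 − (ρ − 1)(lR − lT)/2 = ρ(lT − lR)/2.

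**Simulation of the SAP model.** 10 subjects per sequence, 3000 runs, residues in units of the within-subject SD (assumed):

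| e, lT, lR | ρ | HFA-152a | HFA-134a | Difference | Period term |
|---|---|---|---|---|---|
| 1, 0, 0 | 0 | −0.50 | −0.51 | 0.00 | 0.01 |
| 1, 0, 0 | 0.5 | −0.50 | −0.50 | 0.01 | 0.51 |
| 0, 1, 1 | 0 | −0.50 | −0.50 | 0.00 | 0.01 |
| 0, 1, 1 | 0.5 | −0.50 | −0.50 | 0.00 | −0.50 |
| 1, 1, 1 | 0 | −1.01 | −1.00 | −0.01 | −0.01 |
| 1, 1, 1 | 0.5 | −1.00 | −1.00 | 0.00 | 0.00 |
| 0, 1, 0 | 0 | −0.24 | −0.25 | 0.00 | 0.00 |
| 0, 1, 0 | 0.5 | −0.13 | −0.37 | 0.24 | −0.25 |

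These agree with the formulas. For an assumed 4-point residue, each adjusted change shifts by −2 (training only), −2 (equal carry-over) or −4 (both). Carry-over of HFA-152a only, with ρ = 0.5, moves the contrast by 0.5 × 4/2 = +1. The period term gives no signal when ρ = 0 or when both baselines carry the same residue.

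**What a Day -1 comparison could show.** The 95% half-width of the paired difference is t(n−1) × √(2/n) within-subject SDs:
- n = 20: 0.66
- n = 18: 0.70
- one sequence of 10: 2.262 × 0.447 = 1.01

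With an assumed SD of 6 points, these are about 4.0, 4.2 and 6.1 points. In one sequence, a 4-point residue would be flagged only about 27% of the time.

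**The case against.** The strongest reply is that the plan does not contradict itself. The 7- to 14-day wash-out is written for the gap between periods, after 75 inhalations, and nothing applies it to a training session of nominally five. That stands: a reader might infer that the first baseline breaches the protocol's own wash-out rule, but the documents do not say so. What remains is an unexplained inconsistency between two scans that serve the same purpose, and with the Protocol 1.2 description of baseline.

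Second, a residue is not likely on what is reported. Besides the short residence time, Protocol 1.1 says that dose-limiting non-clinical effects resolve quickly after exposure, and that a 2-hour chamber study at up to 1000 ppm found no exposure-related effect on symptoms or inflammatory markers. This lowers the concern, but none of it measures recovery of clearance.

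Third, a reader might infer that any residue would go wholly unseen. That is too strong. Tables 14.2.1.1.1 and 14.2.1.1.2 and the figures of actual values show Day -1 by treatment. A 4-point residue after HFA-152a only would raise pooled Day -1 retention under HFA-134a by 4/2 = 2 points, which those outputs would display. Training residue and equal carry-over raise both treatments' Day -1 means alike, so they would not stand out there; the listing still holds every scan.

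Fourth, the design already has a wash-out, a repeated baseline and a period-specific covariate. These help, but the baseline is the very quantity in question.

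**Conclusion.** The point holds for each propellant's own change from Day -1. A residue on clearance would bias it at half weight if only the Period 1 baseline carries it, likewise under equal carry-over into Period 2 alone, and in full if both baselines carry it equally.

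It should not be extended to a general claim that the comparison is biased. Training residue is common to both sequences and equal carry-over is balanced, so neither moves HFA-152a minus HFA-134a. Only unequal carry-over does, by ρ(lT − lR)/2 under the assumptions above. A residue lasting to Day 8 is outside this calculation.

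Nor do the documents show that any residue exists. They give no SD, effect size or recovery time for clearance, so the 4-point residue, the SD of 6 and the correlations of 0 and 0.5 are illustrations. The size in this trial is unknown. The case for acting is that the baselines are not on the same footing, no reason is given, and a descriptive check needs no new data.

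**What to change.** 1. **Protocol 6.1.2.4.2, 7.1.1 and 7.1.2.** Reconcile the training-to-V2 interval with the between-period wash-out and the baseline description in 1.2, so that both Day -1 scans have a consistent propellant-free interval, or state why a shorter one is adequate after training. Cost: a slightly longer lead-in for some subjects, or a short justification.

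2. **SAP 2.1.4 and 8.1.** Add one descriptive table of right-lung PPR2 and PPR4 at Day -1 of TP1 and of TP2, with the within-subject difference (TP2 minus TP1) and its 95% CI, overall and by sequence. State beside it that the difference includes any period effect and cannot detect equal residues in both baselines; item 1 is therefore needed as well. Cost: one table from data already collected, with no extra visit or radiation.

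The table should not act as a gate on the analysis. Under no residue, one of the two sequence intervals would exclude zero about 10% of the time for each endpoint. Nor should a notable difference trigger a switch to Period 1 changes alone: a 4-point training residue would then bias each change by −4 instead of −2.
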